- What is the range of mAb TB31F human serum concentrations in subjects receiving five different dosages of the mAb?
- What is the dynamic range of concentration of mAb TB31F associated with SMFA functional activity at specific time points?
- What is the PK profile of this mAb with respect to half-life of serum concentrations that exceed the minimal inhibitory concentration required for >80% inhibition of oocyst development in the mosquito and 80% inhibition of proportion of mosquito infected with one or more oocysts?

An additional consideration was added regarding subcutaneous dosage in group 5, following IV administration in groups 1-4.

- 4) A fixed dose of 100 mg was selected as proof of concept. The dosage of 100 mg mAb TB31F in subjects of 50-90 kg is equivalent to a dosage of 1.1-2 mg/kg. The bioavailability of mAb is estimated to be between 50 and 80% after subcutaneous administration. The subcutaneous dose is therefore expected to approximate to 1 mg/kg IV. Preliminary analysis in group 2 (1 mg/kg) showed that TRA of >95% is maintained up to day 28 after TB31F administration.
- 5) TB31F will be applied in undiluted form for subcutaneous administration (group 5). There are no formal requirements for the upper limit of osmolality of parenteral drugs [20] and administration of mAbs at higher tonicity has shown to improve subcutaneous absorption of monoclonal antibodies [21]. Intramuscular administration of monoclonal antibodies (which is considered more painful than subcutaneous administration) has shown to be safe and tolerable up to 1100mOsm/kg with limited pain and discomfort [22]. It is therefore to be expected that single small (1mL) undiluted doses of TB31F (pH 6.0 and osmolality ~700mOsm/kg) will have acceptable tolerability. Should subcutaneous administration not be tolerated well, a 1:1 dilution with NaCl is described in the Pharmacy Manual.

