### Statistical Software

- Safety data analysis will be performed in IBM SPSS (latest version available), or R.
- SMFA data analysis will be performed in R.
- mAb TB31F pharmacokinetics will be analyzed using standard non-compartmental methods using the Phoenix WinNonlin software package.
- The relationship between plasma mAb TB31F concentrations and transmission reducing activity in SMFA will be assessed using standard compartmental pharmacokinetic models and empirical and mechanistic pharmacokinetic-pharmacodynamic models using the non-linear mixed effects modelling software package NONMEM 7.4, using Piraña 2.9 as an interface and R for data processing.

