#### Efficacy outcome measures:

6. TB31F mAb concentration in serum at different time-points post administration
7. Pharmacokinetic parameters of the TB31F mAb determined by non-compartmental analysis (e.g. maximum concentration ( $C_{max}$ ), terminal half-life ( $t_{1/2}$ ), area under the concentration versus time curve (AUC), volume of distribution ( $V_d$ ) and the absorption rate constant ( $K_a$ ) when TB31F is administered subcutaneously)
8. Transmission reducing activity (TRA) of participant serum at different time-points post administration, quantified as percentage reduction of oocyst densities in the presence of test serum as compared to control serum in standard membrane feeding assays (SMFA)
9. Transmission blocking activity (TBA) of participant serum at different time-points post administration, quantified as percentage reduction in oocyst prevalence in the presence of test serum as compared to control serum in standard membrane feeding assays (SMFA)

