**Efficacy outcome analyses:**

- TB31F antibody prevalence and density will be determined by ELISA; the mean of duplicate concentration estimates is used for analyses. Antibody density will be expressed in µg/mL (outcome measure 6).
- TB31F antibody density will be plotted over time per individual and either as a mean or geometric mean per group. Mixed effects models may be used to investigate the interaction of timepoints and group on TB31F antibody concentration, allowing for subject specific random intercepts to control for the correlation within individuals (outcome measure 6).
- TB31F pharmacokinetics will be analyzed using standard non-compartmental methods to establish the maximum concentration ( $C_{max}$ ), terminal half-life ( $t_{1/2}$ ), area under the curve (AUC  $0-\infty$ ) and Volume of Distribution ( $V_d$ ) for each subject who received mAb TB31F. Additionally, the absorption rate constant ( $K_a$ ) will be determined for group 5 (subcutaneous administration). Geometric mean and geometric coefficients of variation of  $T_{1/2}$  and  $V_d$ , as well as of dose-adjusted  $C_{max}$  and AUC will be reported per dose group and overall (outcome measure 7).
- TRA will be quantified as the relative reduction in oocyst intensity for test samples (one feeder per test sample) compared to pooled naïve serum controls (two feeders). Samples may be tested in one or two independent SMFA experiments. TRA values for each participant and time-point will be estimated using generalized linear models, as previously described (outcome measure 8).

- We may calculate the percentage of individuals per group that have at least 50%, 80% and 90% TRA per timepoint and the percentage of individuals per group with statistically significant TRA at each timepoint. Mean TRA levels may also be calculated per study group per time point and compared between groups (outcome measure 8).

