- The precision of TRA estimates by SMFA decreases with decreasing TRA. Samples with lower levels of TRA (typically below 80%) may thus have relatively imprecise TRA estimates. For some analyses, we may thus use TRA estimates that are inferred from antibody concentration based on the best fit model for the association between antibody concentration and TRA. For this fit, we will use mixed effects models, similar to methods described by Miura et al., adjusting TB31F antibody concentrations measured in serum to reflect whole blood concentrations. These models will be used to find the best fit model for the association between TB31F antibody concentration and TRA and to estimate Inhibitory Concentration values (e.g. IC80, IC50) (outcome measures 7, 8).

Modeled TRA estimates (based on antibody concentration) will be plotted against observed TRA estimates (outcome measure 8).

- TBA will be quantified as the reduction in oocyst prevalence in the presence of test serum as compared to control serum^1 and presented per group and time-point (outcome measure 9).
- The obtained pharmacokinetic and pharmacodynamic data will be further analyzed integrally by means of non-linear mixed effects modeling (outcome measure 7, 8). Using an exploratory approach, we will fit single and multicompartmental methods to the obtained pharmacokinetic data and investigate both linear and non-linear elimination and disposition. Thereafter, we will investigate whether the pharmacokinetics relate with TRA. The developed pharmacokinetic-pharmacodynamic model will be used for *in silico* exploration of:
  - o TB31F dosing regimens needed to achieve at least 80% TRA during an epidemiological relevant time frame (e.g. a typical transmission season of three months)
  - o the effect of monoclonal antibody engineering, resulting in a longer circulation half-life due to a more favorable pH-dependent binding to human neonatal receptor on the dose needed to achieve at least 80% TRA during an epidemiological relevant time frame (e.g. a typical transmission season of three months)
  - o the effect of subcutaneous administration on the dose needed to achieve at least 80% TRA during an epidemiological relevant time frame (e.g. a typical transmission season of three months)

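### The SAP assigns the subcutaneous absorption rate constant (Ka) to non-compartmental analysis and does not commit to estimating bioavailability (F); both belong in the joint compartmental model already planned.

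*SAP*

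**What the plan says.** In the SAP, outcome measure 7 (Efficacy outcome measures) reads "Pharmacokinetic parameters of the TB31F mAb determined by non-compartmental analysis". Its bracketed examples end with Ka for subcutaneous dosing.

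The matching analysis paragraph (Efficacy outcome analyses) begins "TB31F pharmacokinetics will be analyzed using standard non-compartmental methods to establish the maximum concentration" and goes on to half-life, AUC0–∞ and Vd. The next sentence adds that Ka "will be determined for group 5 (subcutaneous administration"), with no other method or software named. Half-life, Vd and dose-adjusted Cmax and AUC "will be reported per dose group and overall (outcome measure 7").

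F is in neither list. It is also absent from Protocol 10.2, which names half-life, AUC, clearance and Vd. It appears only in the dose rationale, Protocol 6.5 point 4: "The bioavailability of mAb is estimated to be between 50 and 80% after subcutaneous administration". From this the protocol expects 100 mg subcutaneously to be close to 1 mg/kg intravenously.

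The SAP also plans a compartmental analysis: "we will fit single and multicompartmental methods to the obtained pharmacokinetic data". Under Statistical Software it names "standard compartmental pharmacokinetic models and empirical and mechanistic pharmacokinetic-pharmacodynamic models using the non-linear mixed effects modelling software package NONMEM 7.4". One stated use of that model is to explore "the effect of subcutaneous administration on the dose needed to achieve at least 80% TRA".

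**The concern.** Ka belongs to an absorption model. Standard non-compartmental output (Cmax, half-life, AUC, terminal volume) does not contain it. An analyst who follows the SAP literally must add a device that the SAP does not name:

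- Curve stripping or Wagner-Nelson on group 5 alone. Both assume one-compartment disposition. Protocol 6.2.2 reports bi-phasic kinetics in rats, and Protocol 10.3 and the SAP allow for multicompartment kinetics in humans. If distribution is visible, these methods read part of it as absorption.
- The moment method, Ka = 1/MAT, where MAT is mean residence time after subcutaneous dosing minus that after intravenous dosing. It needs an intravenous reference group, and the SAP names none for this purpose.

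F is the quantity that links the two routes. Protocol 1.2 says the subcutaneous group was added to help extrapolate to field use, and a simulation of subcutaneous dosing needs a value for F. The SAP does not say that F will be estimated, against which intravenous reference, or with what interval.

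**Working it through.** **1. The plan's own dose figures.** 100/90 = 1.11 and 100/50 = 2.00 mg/kg, which reproduces the protocol's 1.1–2 mg/kg. Multiplying by F gives 0.5 × 1.11 = 0.56 to 0.8 × 2.00 = 1.6 mg/kg intravenous equivalent. At a fixed weight, the assumed F range alone is a 0.80/0.50 = 1.6-fold spread.

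**2. Ka from group 5 alone.**

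*From the documents:* group 5 sampling times (0, 1, 3, 6, 24 h; days 2, 4, 7, 10, 14, 21, 28, 56, 84) and a preliminary half-life of 20.5 days (Protocol 13.2).

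*Assumed:* two compartments, first-order absorption, no noise, V1 = 3.1 L, F = 0.65, and three sets of V2 (L), Q and CL (L/day), each giving a half-life of 20.4–20.7 days:
- A: 2.8, 0.45, 0.225
- B: 2.0, 0.8, 0.18
- C: 1.0, 0.45, 0.14

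*Stripping:* Ka = −slope of ln(back-extrapolated terminal line − C), with the terminal line fitted on days 28–84 and residuals used to day 7.

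*Wagner-Nelson:* fraction absorbed f(t) = [C(t) + λz·AUC(0–t)] / [λz·AUC0–∞]; Ka = −slope of ln(1 − f), using points before f reaches 0.95.

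| True Ka (/day) | A strip / W-N | B strip / W-N | C strip / W-N |
|---|---|---|---|
| 0.15 | 0.30 / 0.30 | 0.19 / 0.18 | 0.17 / 0.17 |
| 0.25 | 0.66 / 0.62 | 0.32 / 0.33 | 0.29 / 0.28 |
| 0.40 | 1.20 / 1.05 | 0.68 / 0.69 | 0.50 / 0.52 |
| 0.60 | 3.4 / 2.2 | 1.40 / 1.35 | 1.04 / 0.87 |

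The overestimate is about 2- to 6-fold in set A, 1.2- to 2.3-fold in B and 1.1- to 1.7-fold in C. With truly one-compartment kinetics (V = 5 L assumed), Wagner-Nelson is within about 4% for absorption half-lives up to 4 days and 12% at 6 days.

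**3. Ka as 1/MAT.** In set A, with the intravenous dose treated as a bolus at the intravenous sampling times, true Ka of 0.15, 0.25, 0.40 and 0.60 comes back as 0.143, 0.232, 0.354 and 0.504: 5–16% low. Precision is the difficulty. In 400 simulated trials with 5 subcutaneous and 20 intravenous subjects (one compartment, 12% assay noise, moderate between-subject variability, true MAT 3.6 days), estimated MAT had a 95% range of −1.9 to 11.2 days and was zero or negative in 11.5% of trials. In the same trials (true Ka 0.277/day) a one-compartment model fit gave 0.21–0.37.

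**4. Precision of F as an AUC ratio.** With s = √ln(1 + CV²), the 95% CI factor is exp(t × s × √(1/5 + 1/n)), where t is the 0.975 quantile on 3 + n degrees of freedom and n is the number of intravenous subjects. For CV = 30%, s = 0.2936. With n = 20, t = 2.069 and the factor is exp(2.069 × 0.2936 × 0.5) = 1.35; if F = 0.65 the interval is 0.48–0.88.

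| Assumed CV | 5 vs 20 (groups 1–4) | 5 vs 5 (group 2) |
|---|---|---|
| 20% | 1.23 | 1.33 |
| 30% | 1.35 | 1.53 |
| 40% | 1.49 | 1.75 |

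**5. The overall summary.** After subcutaneous dosing the non-compartmental volume is Vd/F, so 1/0.8 = 1.25 to 1/0.5 = 2 times Vd. Five of 25 subjects contribute it, so the overall geometric mean rises by 1.25^0.2 = 1.05 to 2^0.2 = 1.15, or 5–15%. Dose-adjusted AUC carries a factor F, so its overall geometric mean falls by 1 − 0.8^0.2 = 4% to 1 − 0.5^0.2 = 13%. Dose-adjusted Cmax is lowered by F and by slow absorption as well.

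**The case against.** The defence is substantial. Stripping and Wagner-Nelson appear in neither document, and the Ka sentence in the analysis section names no method. The moment route is non-compartmental, does not assume one compartment, and has only a small bias without noise. The size of the stripping error depends on V2 and Q, which the documents do not give; rat data do not supply them. The NONMEM analysis is tied to outcome measure 7, the item that contains Ka, and can estimate both Ka and F. Dose-adjusted AUC is already reported per group, so anyone can form the ratio.

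All of this stands, and it rules out two stronger readings. A reader might infer that non-compartmental analysis cannot give Ka, so the reported value will be wrong. That does not follow: a Ka can be obtained under added assumptions, and the method is unspecified. A reader might also infer that the trial never examines F, or that the subcutaneous simulation must rest on the assumed 50–80%. The documents do not say so. That range belongs to the advance dose rationale, whereas the simulation uses a model fitted to the data obtained.

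What remains is that outcome measure 7 names non-compartmental analysis as the source of Ka, no passage reassigns it to the model, and no passage commits to F.

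**Conclusion.** The point holds as a wrong assignment and an uncommitted estimand. The available non-compartmental routes to Ka are either open to upward bias (about 1.1- to 6-fold for group 5 alone, if disposition is two-compartment) or very imprecise with five subjects (1/MAT). The bias range rests on assumed V1, V2, Q, CL and Ka. It is small if disposition is close to one-compartment, so no single multiple should be quoted. F can be estimated from the planned data, with a CI factor of 1.23–1.49 against all intravenous groups at an assumed CV of 20–40%. That is wide, but it would check the 50–80% assumption directly. Pooling group 5 into the overall figures shifts Vd and AUC by roughly 4–15% if F lies in that range.

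Severity is minor to moderate: the endpoint is secondary and descriptive, the group has five subjects, and no decision rule depends on Ka or F.

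**What to change.** In the SAP:

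1. Remove Ka from the non-compartmental list in outcome measure 7 and in the analysis paragraph.
2. State that Ka and F are estimated, with 95% CIs, in the planned NONMEM model fitted jointly to groups 1–5, with disposition shared with the intravenous groups.
3. Add F as the ratio of geometric mean dose-normalised AUC0–∞, group 5 to groups 1–4, with a 95% CI. Use group 2 as the reference if kinetics are not dose-proportional. State the dose unit used, because groups 1–4 are dosed by weight and group 5 is not.
4. Keep Cmax and add Tmax as non-compartmental descriptors of absorption.
5. Label the group 5 volume as Vd/F, and leave group 5 Vd and dose-adjusted AUC and Cmax out of the overall summary.

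The cost is SAP wording and one added ratio, with no new samples or visits. The downsides are that Ka becomes model-based and that F will be imprecise, most of all if only group 2 serves as the reference (a factor of 1.53 at a CV of 30%).

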3. STUDY DESIGN

This first-in-human phase 1 trial is a proof-of-concept study whose purpose is to establish the safety and tolerability of TB31F administration in healthy subjects. The secondary objective of this trial is to quantify and measure the serum concentration and functional activity of TB31F in this setting. The trial is not designed to predict drug accumulation in humans upon repeated dosing, as this will be considered in the future with product characteristics that include improved potency and half-life extension strategies.

While we cannot predict with confidence the safety in human subjects, we have adopted a staggered trial design with escalating dosages of mAb TB31F and a single subcutaneous dosage of mAb TB31F. The trial will be carried out by the Radboud University Medical Center (Radboudumc). Four groups will receive a single dose of mAb TB31F administered by intravenous infusion and one group will receive a single dose of mAb TB31F administered subcutaneously. Group 1 (n=5) will receive 0.1 mg/kg TB31F, group 2 (n=5) will receive 1 mg/kg TB31F, group 3 (n=5) will receive 3 mg/kg TB31F, and group 4 (n=5) will receive 10 mg/kg mAb TB31F by intravenous infusion. Group 5 (n=5) will receive 100mg subcutaneously, divided equally between injection sites. Twenty-five (n=25) subjects will be enrolled, as well as 1 reserve subject per group.

TB31F administration within each group will be staggered such that the first subject in each group will be administered mAb TB31F and observed for the occurrence of any AEs. The second subject in each dose group will not receive their dose of TB31F sooner than 2 days after the first subject has received TB31F (Figure 3). For group 1, there will be a minimum of 48 hours between TB31F administration to each subsequent volunteer. For groups 2-5, the remaining three subjects in each dosage group will receive their TB31F dose no sooner than 2 days after the second subject has been administered TB31F, with at least a one-hour interval in administration of TB31F between each subject.

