## Introduction

TB31F is a first-in-human phase I, open-label, single-site, dose-escalation study to determine the safety, tolerability and pharmacokinetics of the monoclonal antibody (mAb) TB31F. MAb TB31F will be administered intravenously (i.v.) (groups 1-4) or subcutaneously (group 5) as a single dose to 25 healthy adults, 5 groups of 5 volunteers. The study participants are followed for a 12-week period after infusion; samples are collected following a scheme defined in the study protocol.

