**Analyses in relation to endpoints**

**Safety outcome analyses:**

- For each solicited (local or general) adverse event type, the number and proportion of subjects experiencing that AE within the Protocol-defined timeframe will be tabulated by severity grade for each dose group and for the entire study population. This will also be tabulated for subjects experiencing any solicited local, any solicited general and any solicited AE (see example table below). Where applicable, we will compare these proportions between groups. Relatedness (possibly, probably or definitely) of solicited AEs to TB31F administration may also be presented. (Outcome measures 1 and 2).
- For each unsolicited adverse event type (categorized by ICD-10), the number of events per dose group and overall study population will be described categorized by severity grade and relation to TB31F administration. (Outcome measure 4).
- The proportion of individuals with grade 1, 2 and 3 adverse events may be compared between groups (Outcome measures 1,2,4) .
- The total number of grade 1, 2 and 3 adverse events as count data may be compared between groups.
- Individual serious adverse events (SAEs) will be summarized, including relatedness to TB31F administration (Outcome 5).
- Withdrawals due to AEs/SAEs will be summarized per group.

Table - Descriptive statistics for subjects experiencing solicited AEs

|               |           | Group 1   |   | Group 2   |   | Group 3   |   | Group 4   |   | Group 5   |   | All       |   |
|---------------|-----------|-----------|---|-----------|---|-----------|---|-----------|---|-----------|---|-----------|---|
|               |           | #Subjects | % | #Subjects | % | #Subjects | % | #Subjects | % | #Subjects | % | #Subjects | % |
| Local AE1     | Grade 1   |           |   |           |   |           |   |           |   |           |   |           |   |
|               | Grade 2   |           |   |           |   |           |   |           |   |           |   |           |   |
|               | Grade 3   |           |   |           |   |           |   |           |   |           |   |           |   |
|               | Any grade |           |   |           |   |           |   |           |   |           |   |           |   |
| Local AE2     | Grade 1   |           |   |           |   |           |   |           |   |           |   |           |   |

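### The SAP's overall row for Vd, dose-adjusted Cmax and dose-adjusted AUC has no route restriction and, as written, mixes 5 subcutaneous with 20 intravenous subjects

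*SAP*

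**What the plan says.** The SAP (Efficacy outcome analyses, outcome measure 7) derives Cmax, terminal half-life, AUC to infinity and Vd by non-compartmental methods "for each subject who received mAb TB31F". It singles out group 5 only to add an absorption rate constant. It then summarises half-life, Vd and dose-adjusted Cmax by geometric mean and geometric CV, "and AUC will be reported per dose group and overall (outcome measure 7").

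The Introduction gives the make-up of the trial: TB31F is "administered intravenously (i.v.) (groups 1-4) or subcutaneously (group 5) as a single dose to 25 healthy adults, 5 groups of 5 volunteers". That is 4 × 5 = 20 intravenous and 5 subcutaneous subjects.

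The SAP does not define the word overall for this summary and has no PK table shell. Under Safety outcome analyses it uses parallel wording for everyone in the trial: "the number of events per dose group and overall study population will be described". The solicited-AE table shell there has an All column beside Groups 1–5. Protocol section 10.2 reports PK by dose group, with no overall row and no route restriction.

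Protocol section 6.5 expects incomplete absorption: "The bioavailability of mAb is estimated to be between 50 and 80% after subcutaneous administration".

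**The concern.** Dividing by dose removes differences in the amount given. It does not remove differences in the fraction that reaches the circulation. After intravenous dosing, non-compartmental analysis estimates Vd and AUC/dose. After subcutaneous dosing, without a bioavailability correction, it estimates Vd/F and F × AUC/dose. The subcutaneous Cmax/dose is reduced by F and again by slow absorption. A row over all 25 subjects therefore averages two different parameters under one label. Its centre depends on F and on the arbitrary 20:5 split, and its geometric CV combines a route difference with between-subject variability.

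Pharmacokinetics is a secondary objective, and an overall row is easily read as the single summary of volume, dose-normalised exposure and variability. The per-group rows are not affected. Nor is overall half-life, provided absorption is faster than elimination.

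**Working it through.** The plan gives no figure for the overall row, so there is none to reproduce. Its nearest figure is the dose equivalence in protocol section 6.5: 100 mg is 100/90 = 1.1 to 100/50 = 2.0 mg/kg for 90 to 50 kg, as stated there.

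**Inputs**
- n = 20 intravenous and 5 subcutaneous (SAP Introduction).
- F = 0.5 to 0.8 (protocol 6.5; a general antibody estimate, not a TB31F value).
- Assumed: linear pharmacokinetics, one common dose-adjustment unit for both routes, and a within-route CV of 20% or 30%. The documents give no CV.

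**Centre of the row.** A geometric mean over 25 subjects, 5 of whose values are multiplied by a ratio r, shifts by r^(5/25).
- AUC/dose, r = F: 0.5^0.2 = 0.871 and 0.8^0.2 = 0.956, so 13% to 4% low.
- Vd, r = 1/F: 1/0.871 = 1.149 and 1/0.956 = 1.046, so 15% to 5% high.
- Cmax/dose: low by at least the same 4–13%, because absorption slower than the infusion can only lower the peak. The extra amount needs absorption and distribution assumptions from outside the documents, so no figure is given.

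**Spread of the row.** With s² = ln(1 + CV²), the expected log-scale sample variance at a fixed 20:5 split is s² + [(20 × 5/25)/24] × (ln F)² = s² + (ln F)²/6. The reported CV is √(exp(variance) − 1).

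| Within-route CV | s² | Reported CV, F = 0.8 | Reported CV, F = 0.5 |
|---|---|---|---|
| 20% | 0.0392 | variance 0.0475, CV 22% | variance 0.1193, CV 36% |
| 30% | 0.0862 | variance 0.0945, CV 31% | variance 0.1663, CV 43% |

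**Shift against precision.** With the split fixed by design, the log-scale SE of the pooled mean is √(s²/25) whatever F is. The log-scale shift is 0.2 × |ln F| = 0.0446 (F = 0.8) or 0.1386 (F = 0.5).
- CV 20%: SE = 0.0396 (4.0%), so the shift is 1.1 to 3.5 SE.
- CV 30%: SE = 0.0587 (6.0%), so the shift is 0.8 to 2.4 SE.

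**Does dropping five subjects cost more than it gains?** If the row is meant to describe intravenous AUC/dose or Vd, compare log-scale root mean square error: pooled = √(s²/25 + (0.2 ln F)²), intravenous-only = √(s²/20).

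| Within-route CV | Intravenous-only | Pooled, F = 0.8 | Pooled, F = 0.5 |
|---|---|---|---|
| 20% | 0.044 | 0.060 | 0.144 |
| 30% | 0.066 | 0.074 | 0.151 |

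Intravenous-only is the smaller in all four cases.

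**The case against.** The strongest reply is that this is an undefined word rather than an error. In the safety and ADA sections the SAP spells out that it means the whole study population. Here it says only overall, straight after dose-adjusting, which is the step that lets intravenous dose levels be combined. An intravenous-only row may have been intended. That is possible, but the same bullet computes the parameters for every dosed subject and restricts nothing, so a programmer following it would pool 25.

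Second, nothing depends on the row. Protocol 10.2 does not call for it, groups 1–5 are shown separately, and exploration of subcutaneous dosing goes through the population model. This stands, and it is why the point is minor.

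Third, calling the shift a bias presumes that the row estimates the intravenous value, which the SAP never says. This stands in part: the root mean square errors apply only to that target. Without it, Vd and Vd/F are still different parameters, and their average describes neither route.

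Fourth, the size rests on assumptions. At F = 0.8 the effects are slight: AUC/dose 4% low, and a 20% CV reported as 22%. The AUC and Cmax figures also need a common dose unit, although groups 1–4 are dosed in mg/kg and group 5 in mg. Linearity is also open, since the modelling will "investigate both linear and non-linear elimination and disposition". If the kinetics are non-linear, an intravenous-only row still mixes dose levels. These points limit the figures but give no reason to mix routes as well.

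**Conclusion.** The concern holds. Followed as written, the overall row for Vd, dose-adjusted Cmax and dose-adjusted AUC combines 20 intravenous values with 5 subcutaneous values of different parameters, although the protocol itself expects F well below 1.

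Under F = 50–80%, linear kinetics and a common dose unit, the row's AUC/dose is 4–13% low and its Vd 5–15% high against the intravenous value. Cmax/dose is low by at least as much as AUC/dose. The geometric CV is inflated slightly at F = 0.8 and markedly at F = 0.5.

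This is a minor but real fault in a descriptive secondary summary. It should be corrected, but it touches no test, decision or dose choice in either document.

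**What to change.** In the outcome measure 7 bullet of the SAP:

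- State that overall Vd, dose-adjusted Cmax and dose-adjusted AUC cover groups 1–4 (intravenous) only.
- Report group 5 separately for these parameters, with its volume labelled Vd/F.
- Overall half-life may stay pooled, on the condition that absorption in group 5 is faster than elimination.
- As an optional clarification, state the dose-adjustment unit.

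The cost is SAP wording and table labels, with no new data or visits. For three parameters the overall row falls from 25 to 20 subjects. The SE of the geometric mean then rises from 4.0% to 4.5% at an assumed CV of 20%, or from 6.0% to 6.8% at 30%.
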